Co-investigator	[name] Malaria Elimination Programme E-mail : [contact] [name] Zanzibar Malaria Elimination Programme E-mail : [contact]
Co-investigator	[name], MD, PhD, DTM&H, Karolinska Instituttet, stockholm, Sweden. E-mail: [contact] [name] [name], MD, PhD, DTM&H, Uppsala University, Uppsala, Sweden. E-mail: [contact]
Participating institutions	Mnazi mmoja hospital Zanzibar Malaria Elimination Programme Karolinska Institutet, Stockholm, Sweden Uppsala University, Uppsala, Sweden
Study dates	April to October 2017
Sponsors	Ministry of Health, Zanzibar, Tanzania [name]. Global Fund: QNB-M-MOH Karolinska Institutet and Uppsala University, Sweden
Clinical trial registration	The study will be registered at ClinicalTrials.gov prior to commencement of the trial

SUMMARY

Title: Efficacy and safety of artesunate + amodiaquine combined with a single low dose of primaquine (0.25 mg/kg) for the treatment of uncomplicated *Plasmodium falciparum* malaria in Zanzibar.

Background: Zanzibar introduced artemisinin combination therapy (ACT) for the treatment of uncomplicated *P. falciparum* malaria in 2003 with artesunate + amodiaquine as first-line treatment. Following wide scale deployment of ACT together with strengthened vector control with long lasting insecticidal nets (LLIN) and indoor residual spraying (IRS) the burden of malaria has declined markedly in Zanzibar to a level equivalent with malaria pre-elimination. Artesunate+amodiaquine has previously shown to be safe and highly efficacious with polymerase chain reaction (PCR) corrected cure rates >90% by day 42 in clinical trials conducted 2003/4 and 2005. Recently, and in line with WHO recommendations for low transmission settings, a single low dose of primaquine (0.25 mg/kg), a *P. falciparum* gametocytocidal drug, has been introduced as policy. However, no updated efficacy data of the firstline treatment for uncomplicated malaria are available from Zanzibar.

Objective: To assess the efficacy and safety of artesunate+amodiaquine combined with a single low dose of primaquine (0.25 mg/kg) for the treatment of uncomplicated *P. falciparum* malaria in Zanzibar.

Methods: A one-arm prospective antimalarial drug efficacy trial will be conducted.

Participants will be recruited from febrile patients, i.e. documented axillary temperature ≥37.5 °C or history of fever during the past 48 hours, of 3 months and above years old, presenting at primary health care facilities in Zanzibar, with microscopy confirmed uncomplicated *P. falciparum* infection. Enrolled patients will receive directly observed treatment with artersunate + amodiaquine once daily for 3 consecutive days according to the national malaria treatment guidelines. A single low dose of primaquine (0.25 mg/kg) will be administered together with the first artesunate + amodiaquine dose. Clinical and parasitological as well as safety parameters will be monitored over a 28-day follow-up period. The study will be conducted between April and October 2017. The results will be used to assist the Zanzibar Ministry of Health in assessing the current national treatment guidelines for uncomplicated *P. falciparum* malaria.

BACKGROUND

Zanzibar was among the first regions in sub-Saharan Africa to introduce artemisinin combination therapy (ACT) for the treatment of uncomplicated *P. falciparum* malaria in 2003 as a response to reports of unacceptable high treatment failure with chloroquine. The wide scale deployment of ACT, free of charge to all malaria patients through public health care facilities, together with strengthened vector control with long lasting insecticidal nets (LLIN) and indoor residual spraying (IRS) have resulted in a marked decline in burden of malaria in Zanzibar (Bhattarai et al 2007).

Since September 2003 the first line-treatment of uncomplicated malaria in Zanzibar is artesunate + amodiaquine. Presently, a fixed dose combination of artesunate + amodiaquine (Artesunate Amodiaquine Winthrop[®], Sanofi Aventis), prequalified by the WHO, is deployed for treatment of uncomplicated malaria infection once daily for 3 consecutive days in all primary health care facilities. The present alternative treatment in case of known intolerance to artesunate + amodiaquine is artemether-lumefantrine (ALU); however, in some cases other artemisinin based combination therapy are prescribed particularly in private facilities. ALU is rarely used. Artesunate injection is a drug of choice for severe malaria, if not available Artemether or quinine are acceptable alternatives, whereas Artesunate and amodiaquine is also used for intermittent screening and treatment in pregnancy (IST).

Artesunate + amodiaquine as well as artemether-lumefantrine have previously shown to be safe and highly efficacious, with polymerase chain reaction (PCR) corrected cure rates >90% by day 42 in clinical trials conducted 2003/4 ([name] et al 2005) and 2005 (Holmgren et al 2007) for the treatment of children with uncomplicated *P. falciparum* malaria in Zanzibar. Zanzibar has recently, and in line with WHO recommendations for low transmission settings, introduced as policy for uncomplicated malaria a single low dose of primaquine (0.25 mg/kg), a *P. falciparum* gametocytocidal drug, in addition to standard ATC. However, no recent efficacy data of the presently recommended first-line treatment are available.

The aim of this study is therefore to provide policymakers with updated efficacy and safety data of artesunate + amodiaquine in combination with a single low dose of primaquine (0.25 mg/kg) and data on genetic markers of ACT tolerance/resistance, proposed as an early warning system for development and spread of antimalarial drug resistance, in Zanzibar. The study protocol is based on the new WHO guidelines for surveillance of antimalarial drug efficacy (WHO 2014).

OBJECTIVES

The general objective of this study is to assess the therapeutic efficacy and safety of artesunate + amodiaquine combined with a single low dose of primaquine (0.25 mg/kg) for the treatment of uncomplicated *P. falciparum* malaria patients in Zanzibar.

The specific objectives are:

- to determine the clinical and parasitological efficacy of artesunate + amodiaquine and primaquine in the treatment of uncomplicated *Plasmodium falciparum* infection;
- to differentiate recurrent infections during follow-up, i.e. recrudescence from new infections, by PCR analysis;
- to evaluate the incidence of adverse events, particularly with regards to potential

hematological adverse events of primaquine; and

- to determine the polymorphism of molecular markers associated with artesunate + amodiaquine tolerance/resistance.
- to formulate recommendations, which will enable the Zanzibar Ministry of Health to make informed decisions about whether the current national antimalarial treatment guidelines should be updated or not.
- To determine efficacy rate of the first line treatment compared to the first efficacy trial thirteen years ago.

3. METHODS

3.1 Study design and clinical trial registration

This surveillance study is designed as a one-arm prospective evaluation of the clinical and parasitological responses to directly observed treatment for uncomplicated malaria WHO, 2003 and 2009). People with uncomplicated malaria, who meet the study inclusion criteria will be enrolled, treated on site with artesunate + amodiaquine and a single low dose of primaquine (0.25 mg/kg) and monitored for 28 days. The follow-up will consist of a fixed schedule of check-up visits and corresponding clinical and laboratory examinations. On the basis of the results of these assessments, the patients will be classified as having therapeutic failure (early or late) or an adequate response. Blood samples from patients experiencing therapeutic failure during the follow-up period will be used to estimate the efficacy of the study drugs based on PCR analysis to distinguish between recrudescence (treatment failures) and reinfection (new infections).

This study will be registered at the ClinicalTrials.gov registry platform before commencement of the trial.

3.2 Study sites

The study will screen patients from 14 selected primary health care facilities (see below) in three different three districts of Zanzibar Islands. These facilities will classified as sattelite study sites and recruitment sites. The satellite facilities will be used for initially screening the eligible patients for the inclusion criterias; these includes signs of uncomplicated malaria, positive confimed using malaria Rapid Diagnostic Tests (mRDT), verbal consent for patients above 18 years and verbal asent from parent (s) for the children below 18 years. Any patient who will show eligibility to participate will be transferred to the recruitment sites.

In each district there will be one recruitment study site of which patients will enrolled in based on the set eligibility criteria. Recruitment sites will equiped with microscope with all consumables, haemaque machine for hemaglobin and well trained technicians that recently has undergone a malaria microscopy refresher course to ensure the highest possible quality of microscopy service throughout the study. Responsible Clinicians will be oriented to the study protocol and assigned to recruit, treat, fill the case record form and follow up details inclusion and exclusion criterias.

The 14 primary health care facilities included in the study are from 2 districts (West and Central and one district (Micheweni) of Unguja and Pemba Islands respectively. These facilities were chosen based on higher malaria cases detected on the previous three months

but also because they are located nearby to the one of the proposed recruitment sites. The proposed study sites are the following:

Micheweni, Tumbe, Shumba viamboni (Micheweni District); Chukwani, Kizimbani, Shakani, Kombeni, Bububu, Selem, Magogoni (West District); Mwera, Miwani, Machui and Uzini (Central District).

Proper communication between settalites and recruitment study sites will be established to make sure all screened patients with initial eligible criterias to be able transferred to the recruitment sites for detailed screening for study inclusion criterias. All eligible patients will be given written consent and asent forms to sign at the recruitment sites. Treatment, observation and follow up to the enrolled patients will be conducted in all three proposed recruitment study sites namely Micheweni (Pemba) and Bububu Jeshini and Uzini of Unguja Island.

3.3 Study population

The population will consist of patients of all ages presenting at the study sites with symptom and signs compatible with uncomplicated P. falciparum malaria. All adult patients will be informed about the study and asked to sign the consent form for participation prior to enrolment. Parents or guardians will give informed consent on behalf of their children. Children over 12 years of age will sign an informed assent form.

3.4 Timing and duration of study

The study is planned to be conducted for six months, from April to October 2017.

3.5 Inclusion criteria

- Age 3 months and above;
- P. falciparum infection detected by mRDT and confirmed by microscopy;
- presence of *P. falciparum* malaria asexual parasitaemia (any level);
- presence of axillary \geq 37.5 °C or history of fever during the past 48 hours
- ability to swallow oral medication;
- ability and willingness to comply with the study protocol for the duration of the study and to comply with the study visit schedule; and
- informed consent from the patient or from a parent or guardian in the case of children.

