4. TREATMENT

4.1 Antimalarial treatment

Artesuate + amodiaquine will be administered orally as a fixed dose combination, i.e. Artesunate/Amodiaquine Winthrop®, prequalified by the WHO, at a dose of approximately artesunate 4 mg/kg + amodiaquine 10mg/kg once daily for 3 consecutive days.

Primaquine will be administered orally, i.e. ®, prequalified by the WHO, as a single dose (0.25 mg/kg) together with the first artesunate + amodiaquine dose of approximately artesunate 4 mg/kg + amodiaquine 10mg/kg once daily for 3 consecutive days.

The study drugs, represent the present drugs deployed to public health care facilities by the Zanzibar Ministry of Health.

The investigators will be instructed to record the batch number and expiry date of the test medicines. The correct drug dosages will be determined from the dosing charts (Appendix 3), which are in accordance with the national treatment guidelines in Zanzibar.

All doses of medicine will be administered under direct supervision of a qualified member of the staff designated by the principal investigator. The study patients will be observed for 30 minutes after medicine administration for adverse reactions or vomiting. Any patient who vomits during this observation period will be re-treated with the same dose of medicine and observed for an additional 30 minutes. If the patient vomits again after the second study drug administration, he/she will be withdrawn and offered rescue therapy (see below section 4.3 Rescue treatment).

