Appendix 3. DOSING CHART OF ARTESUNATE + AMODIAQUINE AND PRIMAQUINE

A fixed dose combination of artesunate + amodiaquine (Artesunate Amodiaquine Winthrop®, Sanofi Aventis), prequalified by the WHO, will be used as study drug. Tablets containing 25/67.5 mg, 50/135mg and 100/270 mg, base of artesunate/amodiaquine will be administered according to the dosing chart below:

Body	Number of tablets of Artesunate (AS) + Amodiaquine (AQ)								
weight	Day 0	Day 1	Day 2						
<10 kg	1 tab	1 tab	1 tab						
	(AS 25 mg + AQ 67.5 mg)	(AS 25 mg + AQ 67.5 mg)	(AS 25 mg + AQ 67.5 mg)						
10-20 kg	1 tab	1 tab	1 tab						
	(AS 50 mg + AQ 135 mg)	(AS 50 mg + AQ 135 mg)	(AS 50 mg + AQ 135 mg)						
21-30 kg	2 tab	2 tab	2 tab						
	(AS 50 mg + AQ 135 mg)	(AS 50 mg + AQ 135 mg)	(AS 50 mg + AQ 135 mg)						
>30 kg	2 tab	2 tab	2 tab						
	(AS 100 mg + AQ 270 mg)	(AS 100 mg + AQ 270 mg)	(AS 100 mg + AQ 270 mg)						

	DOSAGE AND ADMINISTRATION OF PRIMAQUINE								
	WEIGHT AGE Single low dose [o hrs]								
1	5-9 kg	1-4 yrs	2.5 mg						
2	10-20 kg	5-8 yrs	5 mg						
3	20-40 kg	9-14 yrs	10 mg						
4	>40 kg	15+ yrs	15 mg						

Pediatric dosing of SLD primaquine:

To dissolve tablets in Water:

- a. Based on patients weight dissolve one tablet(s) (15mg) of Primaquine in 5 ml of
- b. Ensure that the solution is thoroughly mixed.
- c. Measure the volume (cc) of solution to give to the participant based on the participant's weight. The drug will be mixed with equal volume of juice to mask its bitter test

Picture 1: Sanofi product, Primaquine phosphate USP Tablets 26.3 mg (15 mg equivalent base)

The extemporaneous preparation should be conducted as follows

- the extemporaneous preparation should be conducted as follows:

 Define number of 15mg (primaquine base) tablets required based on patient's age or weight.

 Crush tablets in mortar with pestle.

 Pour powder into the clean container to be used for dilution (preferably glass container as there is no data on interaction with plastic).

 Based on 15 ml. of water for 1 tablet, measure in a graduated syringe the required volume of water needed to dissolve the tablets. Use a fraction of water from the syringe to rinse the mortar and pestle, and pour contents into the container.

 In the container, mix the powder and fiquid thoroughly with a spoon.

 Leave for 1 minute to rest. Some residuals (exceptients not dissolved such as tale) will appear on the bottom of the container and do not need to be withdrawn.

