 Based on patient's weight, withdraw required volume with graduated syringe, avoiding the exception at the bottom of the container. See table 1 below for examples.

 The prepared solution can be stored in the glass container for a maximum of 3 days at 40°C or 7 days at 30°C, protected from light.

 Do not store the prepared solution inside the syringe as there are no data available on potential interactions between syringe materials and primaquine.

Age (years)	ears) Weight (kg) Dosage (mg) (0.25 x weight)		Volume to be withdrawn (ml) (for a solution of 1mg/ ml)	Syringes recommended for administration		
1	9	2.25	2.25	5 ml		
6	18	4.5	4.5	10 ml		
14	36	9.0	9.0	10 ml (or 20 ml)		

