Appendix 5. CASE SCREENING FORM

Case screening form					
Health centre name:	Study number:				
District:	Patient screening number:				
Sheiha	Date of visit (dd-mmm-yyyy):				
Demographi	c data				
Date of birth (dd-mmm-yyyy): or esti	imated age: in: months or years				
Height (cm): Weight (kg):					
Sex: Male Female					
If female, is the patient pregnant? Yes No Unknow	n				
If pregnant, provide the date of the last menstrual period (dd-	mmm-yyyy):				
Pre-treatment te	mperature				
History of fever in previous 48 h? Yes No					
Axillary temperature: °C					
Screening test for presence of P. falcipa	urum with Rapid Diagnostic Test				
RDT result Positive Negative	re (If negative, patient is not eligible)				
Thick and thin blood smears for estimation	on of P. falciparum parasite counts				
Species: P. falciparum P. vivax P. ovale P. mal	ariae				
Were species other than P. falciparum present? Yes No	o (If yes, patient is not eligible).				
Presence of P. falciparum asexual parasites: Yes No (1	f no, patient is not eligible)				
Presence of P. falciparum gametocytes? Yes No					
Has a blood sample for PCR been collected? Yes No					
Urinary analysis (pregnancy t	test for female patients)				
Result of pregnancy test: Positive Negative Not do	ne (If positive, patient is not eligible)				
Inclusion cr	iteria				
• age 3 months and above					
• mono-infection with P. falciparum detected	by microscopy;				
• presence of P. falciparum malaria asexual p	parasitaemia;				
• presence of axillary ≥37.5 °C or history of	fever during the past 24 hours				
ability to swallow oral medication;					
 ability and willingness to comply with the study protocol for the duration of the study and to comply with the study visit schedule; and 					
• informed consent from the patient or from a	parent or guardian in the case of children.				
Does the patient meet all the inclusion criteria? Yes No	(If no, patient is not eligible)				

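### Appendix 3 gives conflicting primaquine instructions: 20 kg sits in two dose rows, and the tablet is dissolved at two strengths although volumes are printed for only one

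*Combined protocol and SAP*

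**What the plan says.** Section 3.5 sets the lower age limit at "Age 3 months and above", and the screening form in Appendix 5 repeats it ("age 3 months and above"). Neither gives a minimum weight. Section 4.1 states the nominal primaquine dose, "as a single dose (0.25 mg/kg) together with the first artesunate + amodiaquine dose", and then names the source staff are to use: "The correct drug dosages will be determined from the dosing charts (Appendix 3". Section 5.2.2 records weight to the nearest kilogram and uses it to work out the dose.

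Appendix 3 then gives, for primaquine:

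- a band chart: 5-9 kg (1-4 years) 2.5 mg; 10-20 kg (5-8 years) 5 mg; 20-40 kg (9-14 years) 10 mg; above 40 kg (15 years and over) 15 mg;
- a short paediatric recipe: "dissolve one tablet(s) (15mg) of Primaquine in 5 ml of" (the line stops there in the text available), followed by measuring a volume according to weight, with no volumes given;
- a longer recipe: "Based on 15 ml. of water for 1 tablet", in which the number of tablets may be chosen by age or by weight;
- an example table whose dose column is headed "Dosage (mg) (0.25 x weight" and whose volumes are "for a solution of 1mg/ ml".

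**The concern.** These are working instructions for clinic staff at three recruitment sites, and at two points they cannot all be followed. At 20 kg the chart gives two doses. For children who need a solution, the appendix gives two strengths but prints volumes for one. Someone who follows the short recipe and then looks for a volume finds only the table that belongs to the other recipe. The appendix also lets prepared solution be stored for up to 7 days at 30 °C, so the person drawing up a dose need not be the one who mixed it.

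Haematological adverse events of primaquine are a named specific objective. Unintended variation in dose is therefore a safety matter for the child, and it also blurs what the haemoglobin results describe.

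Three smaller points sit beside these. The chart has no row for the lightest eligible infants. Its age column starts at 1 year, although patients are eligible from 3 months and one preparation step allows age to be used. The example doses are not the chart doses.

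**Working it through.** **Inputs.** Chart rows, tablet strength (15 mg base), water volumes (5 ml and 15 ml) and example rows from Appendix 3; nominal 0.25 mg/kg from section 4.1; weight to the nearest kilogram from section 5.2.2.

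**1. The plan's own example figures.** Dose = 0.25 x weight: 0.25 x 9 = 2.25 mg, 0.25 x 18 = 4.5 mg, 0.25 x 36 = 9.0 mg. At 1 mg/ml these are 2.25, 4.5 and 9.0 ml. The example table is reproduced exactly.

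**2. Overlap at 20 kg.** 5 mg / 20 kg = 0.25 mg/kg; 10 mg / 20 kg = 0.50 mg/kg. The ratio is 2. With rounding to whole kilograms, 20 is an ordinary recorded value. The artesunate-amodiaquine chart in the same appendix avoids the problem by using 10-20 and 21-30 kg.

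**3. Two strengths.** 15 mg / 5 ml = 3 mg/ml; 15 mg / 15 ml = 1 mg/ml. The ratio is 3. Using the printed volumes with the 3 mg/ml preparation:

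| Weight | Printed volume | Intended dose | Dose at 3 mg/ml | mg/kg |
|---|---|---|---|---|
| 9 kg | 2.25 ml | 2.25 mg | 2.25 x 3 = 6.75 mg | 6.75 / 9 = 0.75 |
| 18 kg | 4.5 ml | 4.5 mg | 4.5 x 3 = 13.5 mg | 13.5 / 18 = 0.75 |

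With one tablet in 5 ml, the error can be made in full only while the volume needed is at most 5 ml: 5 / 0.25 = 20 kg. At 36 kg the printed 9.0 ml is more than was made, so the mismatch would show itself.

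For comparison, the highest dose the chart itself gives is 0.50 mg/kg (2.5 / 5, 5 / 10, and 10 / 20 in the upper of the two rows). The 0.75 mg/kg from the dilution mix-up lies outside anything the chart allows.

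**4. Lowest weights.** The first row starts at 5 kg. A true weight of 4.5 to 4.9 kg is recorded as 5 kg and has a row, so the gap is at recorded weights of 4 kg or less. An infant of 3-11 months recorded at 5 kg or more has a dose by weight but no age row.

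**5. Chart against examples.** 2.5 / 2.25 = 5 / 4.5 = 10 / 9.0 = 1.11, so the chart is 11% higher at all three printed weights.

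**The case against.** The strongest objection is to the dilution point. Its only source for 5 ml is a line that breaks off in the text available, next to a picture caption and other damaged text. The 15 ml instruction is complete and agrees with the 1 mg/ml heading. Even if 5 ml is right, a threefold error needs someone to use a column labelled 1 mg/ml with a solution of another strength. This stands as a reason to check the source PDF before acting. It does not dispose of the point: the figure and its unit are legible, and the short recipe offers no volumes of its own.

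At 20 kg, it can be said that 0.25 x 20 = 5 mg settles which row is right, and that 0.50 mg/kg is no more than the chart gives at 5 or 10 kg. Both are true. Section 4.1 nevertheless sends staff to the chart, and the chart still prints both doses.

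On the lesser points the objection largely succeeds. Section 4.1 names the charts as the dose source and the second table is offered as examples, so a reader who infers two rival dosing methods goes too far. The difference at the printed weights is 11%, and larger gaps at the lower band edges are ordinary banding. A reader might also infer that all eligible infants under 5 kg, or all under 1 year, have no dose. Rounding and the weight column rule that out, and the severe-malnutrition exclusion removes some of the lightest infants. Any estimate of how far age-based dosing would miss at 2-4 years needs weights by age that the documents do not give.

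Haemoglobin is checked on days 0, 3, 7, 14 and 28 (section 5.2.7). Because primaquine is a single day 0 dose, that schedule can detect an error but cannot prevent it.

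**Conclusion.** The concern holds as a minor dosing-safety correction to Appendix 3. The firm fault is the double entry at 20 kg, a twofold difference at one recorded weight. The larger possible error is the dilution conflict, threefold in children up to 20 kg; it assumes that the 5 ml figure is confirmed, that one tablet is dissolved, and that the printed volumes are used with that solution. The missing row concerns recorded weights of 4 kg or less. The number of such infants is unknown, probably small, and could be none among the planned 90 patients.

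A reader might infer that children will be overdosed, or that the efficacy result is compromised. The documents support neither. They show that an error is possible, not that it will occur. The sample size in section 8.1 rests on an assumed failure rate and a precision, and nothing in the analysis plan depends on these dosing lines.

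**What to change.** In Appendix 3:

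- change the third primaquine row to 21-40 kg; with weights in whole kilograms this leaves no gap;
- check the 5 ml line against the source PDF and keep only the 1 mg/ml preparation (15 ml per tablet);
- state that weight overrides age and that the band chart sets the dose;
- recast the example volumes to the chart doses at 1 mg/ml: 2.5, 5 and 10 ml at 9, 18 and 36 kg.

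In section 3.5 and on the screening form, add a minimum recorded weight of 5 kg. Adding a lower chart row instead would extend primaquine below the chart's lowest weight. Section 4.1 says the charts follow the national guidelines, and nothing in the documents supports going further down.

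The cost is a few lines in Appendix 3 and one line in each of the other two places. The minimum weight means a few infants may not be enrolled; the other changes lose no patients.
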